2.1.3.1 Nonclinical Background

miRagen has conducted *in vitro* and *in vivo* studies to investigate the pharmacology, pharmacokinetics (PK) and toxicology of cobomarsen. Details of nonclinical studies conducted to date are provided in the cobomarsen (MRG-106) Investigator's Brochure.

Cobomarsen regulates miR-155-5p seed-matched target mRNAs in human CTCL cell lines, in a miR-155-5p-dependent and sequence-dependent manner. Inhibition of miR-155-5p by cobomarsen reduces proliferation and cell survival, with induction of apoptosis, in human mycosis fungoides cell lines in a cobomarsen dose responsive manner. Genome-wide expression analysis demonstrates that cobomarsen regulates numerous genes implicated in cell cycle and apoptosis, consistent with the pharmacologic impact on cell survival. A subset of these genes has been identified as potentially translatable biomarkers to monitor cobomarsen activity in clinical samples.

Experience with phosphorothioate and locked nucleic acid (LNA)-modified oligonucleotide drugs has been well described in the literature and much is understood about the relationship between toxicities observed in non-clinical studies and their potential clinical manifestations. Some of the class-related effects of oligonucleotides are known to be species specific, while others are related to PK, including plasma clearance time, and tissue accumulation and clearance. As such, monkeys are considered the most predictive toxicology species for humans because of their phylogenetic similarity to man and the ability to extrapolate plasma concentrations and clearance rates between primates and man on the basis of mg/kg dosing ([Geary et al. 2003](#); [FDA 2005](#); [Yu et al. 2007](#)).

The toxicities observed in 28-day, repeat subcutaneous dose studies conducted in rats administered 10 cobomarsen doses of 3, 8 or 20 mg/kg and in monkeys administered 10 doses of 3, 10 or 30 mg/kg were primarily those expected of LNA-modified phosphorothioate oligonucleotides. The most notable adverse finding in rats was dose dependent (≥ 3 mg/kg) renal proximal tubule degeneration, characterized by vacuolation and fragmentation of the cytoplasm

of convoluted tubule epithelial cells, as well as changes in serum and urinary biochemical markers indicative of mild changes in renal function at doses ≥ 8 mg/kg. These effects were largely reversed by 8 weeks after the last dose. The rat is known to be more sensitive to renal toxicity from a variety of insults, including treatment with phosphorothioate oligonucleotides (Berman et al. 2014). This is confirmed for cobomarsen as no similar changes in renal morphology or parameters of kidney function were observed in monkeys at doses up to and including 30 mg/kg.

In monkeys, follicular atrophy in the thyroid gland with a concurrent decrease in thyroid organ weight was observed after subcutaneous administration of 30 mg/kg in males and ≥ 3 mg/kg in females. Examination of thyroid-stimulating hormone (TSH) plasma levels demonstrated that this finding did not result in a significant difference in individual monkey's TSH levels between predose Day 1 and Day 28. Furthermore, no clinical indications of gross metabolic imbalance were observed in the monkeys over the course of the study. Following the 28-day recovery period, there was evidence of partial recovery in both incidence and severity of the thyroid atrophy and organ weight. No similar changes in the thyroid were observed in the rat at doses up to 20 mg/kg.

In monkeys, a single 30 mg/kg dose administered as a subcutaneous injection or a 1-minute intravenous bolus injection was well tolerated, with no clinically significant effects on coagulation or complement activation. Transient increases in liver transaminases (< 5 -fold in aspartate aminotransferase [AST] and < 3 -fold in alanine aminotransferase [ALT]), fibrinogen (< 2 -fold) and creatine kinase (CK; < 5 -fold intravenous and < 34 -fold for subcutaneous dosing) values were observed 24 hours postdose but returned to within the normal range by Day 7, the next time point evaluated. These clinical pathology findings were similar between intravenous bolus and subcutaneous dosing suggesting that the increased C_{max} following intravenous injection did not contribute to the transient effects.

Cobomarsen is considered to have a very low risk of genotoxicity based on literature reports and published regulatory opinion regarding the genotoxic potential of oligodeoxynucleotides (EMA/CHMP/SWP/199726/2004) and LNA-containing oligonucleotides (Guérard et al. 2017).

Cobomarsen has recently been evaluated for potential genotoxicity using standard *in vitro* testing methods, including the bacterial reverse mutation (Ames) assay and the micronucleus assay in human peripheral blood lymphocytes. The negative results of these studies confirm that the genotoxicity risk of cobomarsen is very low.

2.1.3.2 Clinical Background

Cobomarsen is being evaluated in a Phase 1 clinical trial to investigate its safety, tolerability and PK, as well as exploratory measures of pharmacodynamics (PD) and efficacy in subjects with CTCL, mycosis fungoides subtype. The study has also enrolled a limited number of subjects with chronic lymphocytic leukemia (CLL), diffuse large B-cell lymphoma (DLBCL) and adult T-cell leukemia/lymphoma (ATLL). Details of the Phase 1 clinical trial results are provided in the cobomarsen (MRG-106) Investigator's Brochure.

Study MRG106-11-101 has completed enrollment of subjects who had prior treatment for CTCL, mycosis fungoides subtype, stages I, II or III. As of 23 July 2019, 6 subjects with CTCL have been treated in Part A with 75 mg cobomarsen by intratumoral injection, and 37 subjects with CTCL have been treated in Part B with 300, 600 or 900 mg cobomarsen by subcutaneous injection, or intravenous infusion or injection. Of note, 2 subjects that had completed Part A were re-enrolled in Part B (with new unique identification numbers) following an 8-week washout period, as permitted in the protocol. In addition, cobomarsen has been explored in other indications and at additional dose levels, as detailed in the Investigator's Brochure.

Overall, the study treatment has been well tolerated. The majority of AEs have been mild or moderate in severity (grade 1 or 2) and there have been no safety signals indicative of clinically significant adverse effects on renal, liver, coagulation, platelets or thyroid function at the dosing regimens evaluated to date. Two subjects experienced dose-limiting toxicities (pruritus and disease flare) resulting in study discontinuation, per protocol. Ninety-two percent (92%) of subjects treated with systemic administration showed improvement in skin disease as measured by the mSWAT score. Sixty-three percent (63%) of subjects treated with 300 mg IV infusion (5 of 8 subjects) achieved a partial response. Being well tolerated, this dose and mode of administration has been selected for the SOLAR trial. Full details on safety and efficacy of cobomarsen in CTCL are found in the Investigator's Brochure.

Pharmacodynamic effects of cobomarsen were assessed in lesion biopsies taken before and after treatment in both parts of the study. In Part A of the clinical trial, high levels of cobomarsen (48-204 µg per gram of tissue) were detected in injected tumors 24 hours after the last dose. Accumulation of cobomarsen was also observed in a lesion distant from the site of injection at low levels (4 µg per gram of tissue). Analysis of injected tumors also indicated an increased expression of several direct targets of miR-155, suggesting that the drug may be inhibiting its intended molecular target. A similar pattern of gene regulation was observed in a lesion not directly injected with drug that had 4 µg cobomarsen per gram of tissue, suggesting the minimum effective dose level in skin lesions may be near this level. After treatment, histology

revealed fewer cancerous cells or a reduction in cancer cell density or depth in most patients. Cobomarsen was also measured in skin biopsies collected from systemically-treated patients in Part B, at doses ranging from 300 to 900 mg. Levels measured showed a mean of 12 µg per gram of tissue, with no clear dose response relationship. Similar patterns of cobomarsen target-gene expression changes were observed in patient biopsies after systemic dosing as were seen in the Part A lesions.

In general, there has been no indication that cobomarsen is affecting the general leukocyte populations in patients that have been treated for up to 18 months except for an increase in natural killer (NK) cells in patients receiving 900 mg doses by multiple routes of administration. Analysis of the functional T-cell subsets have demonstrated that chronic dosing of cobomarsen does not affect the proportions of naïve, effector, and central or effector memory CD4+ and CD8+ T-cells, and the expected expansion and contraction of these effector cells occurs as would be expected during documented common respiratory or skin infections that occurred in several patients during the course of cobomarsen treatment. For full details on pharmacodynamic effects of cobomarsen, please refer to the Investigator's Brochure.

Analysis of cobomarsen clinical PK data reveal biphasic plasma concentration time curves, indicative of multi-compartmental pharmacokinetics. Apparent half-lives ($t_{1/2}$) measured over the first 24-hours were similar for all routes of administration (ROA), ranging from 5.0 to 8.2 hours. Trough plasma samples collected once a month during prolonged administration of cobomarsen generally increased from the first extension cycle sample collection over the next one to two cycles, where they achieved maximum concentrations and then plateaued or declined over subsequent cycles. This may indicate steady state concentrations being achieved after 3 or 4 cycles of dosing, or after approximately 12-16 weeks of regular cobomarsen administration, suggesting a terminal elimination half-life of approximately 2.5 to 3 weeks. Despite the observed differences in C_{max} and T_{max} , dose normalized systemic exposure ($AUC_{0-24}/Dose$) for all dose levels in the intratumoral, subcutaneous, and intravenous 2-hour infusion cohorts were similar, demonstrating good dose proportionality across those ROAs and dose concentrations. Accumulation ratios (multiple dose $C_{max}/$ first dose C_{max} or multiple dose $AUC_{0-24}/$ first dose AUC_{0-24}) indicated no significant accumulation at the 900 mg dose level for any route of administration. For full details on PK profile of cobomarsen in CTCL, please refer to the Investigator's Brochure.

2.1.4 Active Control: Vorinostat

Vorinostat is a histone deacetylase (HDAC) inhibitor approved in the US, Canada and Australia for the treatment of CTCL. This drug is not approved in Europe, and thus remains an investigational product for sites in that region. Complete information on vorinostat, including risks, precautions and adverse effect profile are included in the package insert.

2.2 Scientific Rationale and Dose Selection

Based on the nonclinical and clinical data collected to date, cobomarsen is hypothesized to offer clinical benefit to subjects with MF. The current protocol is a randomized, open-label, parallel-group, active comparator, multi-center, outpatient efficacy study designed to determine the efficacy, safety, and PK of cobomarsen compared with vorinostat in subjects with MF.

Due to a lack of in vivo preclinical models to help define the optimal dose and route for cobomarsen administration, skin lesion biopsies have been collected from a subset of Phase 1 human clinical trial participants dosed with cobomarsen by intralesional injection or systemically by the subcutaneous (SC) or intravenous (IV) routes at three dose levels. These samples are being analyzed for drug concentration and pharmacodynamic activity through molecular analysis of gene expression changes. The results obtained to date suggest that cobomarsen drug levels in individual lesions are highly variable from subject to subject, possibly due to differences in lesion morphology (patch, plaque, tumor) and the vascularity at each biopsy site. The cobomarsen concentration in lesion biopsies collected 24 hours after the last dose ranged from 48.6 to 206 $\mu\text{g/g}$ after multiple 75 mg doses administered by direct intratumoral (IT) injection and from 3.10 to 53.2 $\mu\text{g/g}$ after systemic administration of multiple doses by SC, IV infusion or IV bolus. Based on this small data set, there is not a strong correlation between dose or route of administration and skin biodistribution in systemically treated subjects. However, gene expression analysis demonstrates that concentrations as low as 3 $\mu\text{g/g}$ tissue (0.6 μM) are sufficient to provide pharmacodynamically relevant exposure to the drug in the skin lesions of mycosis fungoides patients. The pharmacodynamic response to cobomarsen was evaluated by measuring the levels of approximately 600 mRNAs in skin lesion biopsies collected from study subjects before and after cobomarsen administration. This panel of mRNAs was identified in preclinical studies as potential direct or indirect targets of miR-155-5p based on their coordinated regulation in three MF cell lines following exposure to cobomarsen (refer to IB section 4.1.1.5). The data showed exposure-related changes in gene expression pathways expected to be modulated by inhibiting miR-155 and suggest that effective cobomarsen levels can be reached in MF lesions using either the subcutaneous or intravenous dosing routes and the 300 mg dose level

is sufficient to achieve the desired pharmacodynamic effects. For more details please see the Investigator's Brochure.

The dosing regimen of cobomarsen that will be administered in this study (282 mg active moiety, administered by intravenous infusion, equivalent to 300 mg of the sodium salt form) is based on above pharmacodynamic data, as well as safety and clinical efficacy data from Phase 1 study. This dose and mode of administration was well tolerated in the Phase 1 study in subjects with MF, who received systemic doses of up to 900 mg (sodium salt). The 300 mg 2-hour intravenous infusion dose regimen was selected based on the generally favorable safety and tolerability data from the ongoing Phase 1 trial. Additionally, compared to the 600 and 900 mg doses, the 300 mg dose appeared to have similar PD and clinical effects. For further efficacy data, please see Investigator's Brochure.

Vorinostat was selected as the active comparator. As this clinical trial will be conducted at multiple sites within the European Union, North America and Australia, it is necessary to select an active comparator that is acceptable for use in all regions, but that is not first line of treatment in any region, as this would exclude many patients from participating in the study. Vorinostat is more typically used as a second-line systemic treatment in the US, Canada and Australia and is not an approved therapy in the European Union. Hence, the majority of the indicated study population in all regions will not have had previous exposure to the drug.

Vorinostat is an HDAC inhibitor, a class of small molecules being evaluated in clinical trials for a number of different malignancies. Vorinostat was the first HDAC inhibitor approved by the US Food and Drug Administration (FDA) in 2006 for treatment of cutaneous manifestations in patients with CTCL who have progressive, persistent or recurrent disease on or following two systemic therapies. In two Phase 2 trials, vorinostat was safe and effective at an oral dose of 400 mg/day with an overall response rate at one month of 31% in refractory advanced patients with CTCL, including large cell transformation and Sézary syndrome. Vorinostat also has a significant symptomatic effect on pruritus, a major symptom in this patient population that directly impacts quality of life ([Zinzani et al. 2016](#)). The most frequent side effects of vorinostat include gastrointestinal symptoms, fatigue and thrombocytopenia ([Duvic and Ju, 2007](#)). The safety profile of the drug is well known, with clear guidelines for dose reduction to decrease gastrointestinal side effects (see vorinostat package insert). Vorinostat is one of the drugs considered as standard of care in the US ([Horwitz et al. 2018](#)) and Australia for \geq stage IB disease.

2.3 Potential Risks and Benefits

The potential risks and benefit of cobomarsen treatment are detailed in the Investigator's Brochure. The potential risks and benefit of vorinostat are in the package insert, which provides the full prescribing information for vorinostat in the US.

2.3.1 Known Potential Risks of Cobomarsen

In clinical studies of phosphorothioate oligonucleotides, most of the observed side effects are believed to be hybridization-independent and related to the physical and chemical characteristics of this class of agents. Certain adverse effects have been observed repeatedly during clinical investigations of systemically administered phosphorothioate oligonucleotide drugs, with the most commonly observed side effects including dermatological reactions at subcutaneous injection sites, constitutional symptoms such as fever, chills, and myalgia primarily associated with initial doses, and dose-dependent prolongation of activated partial thromboplastin time (aPTT) when the drugs are given intravenously, but not when administered subcutaneously. In general, these effects are mild and transient, and resolve spontaneously.

In the ongoing Phase 1 study of cobomarsen, there have been no safety signals indicative of clinically significant adverse effects on coagulation, platelets, or renal, liver, or thyroid function at the dosing regimens (300-900 mg) evaluated in CTCL patients. For full details of all cobomarsen Phase 1 safety data (across all indications) to date, refer to the current cobomarsen Investigator's Brochure and any new safety updates.

Potential risks of exaggerated pharmacology of miR-155 inhibition, specifically immunosuppression, have not been observed in the Phase 1 study in CTCL.

2.3.2 Known Potential Benefits of Cobomarsen

The ongoing Phase 1 study in CTCL was designed primarily to evaluate safety, with efficacy collected as a secondary endpoint. Preliminary evidence of antitumor activity has been observed and potentially outweighs the risks and warrants further investigation.

3 STUDY OBJECTIVES AND ENDPOINTS

3.1 Objectives

3.1.1 Primary Objective

The primary objective of the study is to evaluate the efficacy of cobomarsen in subjects with MF.

3.1.2 Secondary Objectives

Secondary study objectives are to:

- Investigate the safety and tolerability of cobomarsen in subjects with MF.
- Characterize the population PK of cobomarsen in subjects with MF.
- During the crossover portion of the study:
 - Evaluate the efficacy, safety and tolerability of cobomarsen in subjects with MF who have shown disease progression following treatment with vorinostat.

3.2 Endpoints

3.2.1 Primary Endpoint

Primary Efficacy Evaluation:

- Proportion of subjects achieving an objective skin response (complete response [CR] or partial response [PR]) of at least 4 months duration (ORR4) using the mSWAT scoring (see [Section 12.4.3](#) and [Appendix F](#)).

3.2.2 Secondary Endpoints

Efficacy measures:

- Progression-free survival (PFS).
- Complete response rate (CRR).
- Time to progression (TTP).
- Time to maximal effect in skin (mSWAT).
- Proportion of subjects achieving $\geq 50\%$ improvement in mSWAT of at least 28-days duration (ORR1).
- Proportion of subjects achieving $\geq 50\%$ improvement in mSWAT from baseline at 28 days and at 4 months.
- Time to $\geq 50\%$ improvement in mSWAT.
- Duration of response in skin (no progression after achieving $\geq 50\%$ improvement in mSWAT).
- Change in pruritus medication utilization from baseline and incidence of pruritus medication utilization.

- During the crossover portion of the study:
 - Proportion of subjects achieving an objective skin response (complete response [CR] or partial response [PR]) of at least 4 months duration (ORR4) using the mSWAT scoring (see [Appendix F](#)).
 - Progression-free survival (PFS).
 - Complete response rate (CRR)
 - Time to progression (TTP).
 - Time to maximal effect in skin (mSWAT).
 - Proportion of subjects achieving $\geq 50\%$ improvement in mSWAT of at least 28-days duration (ORR1).
 - Proportion of subjects achieving $\geq 50\%$ improvement in mSWAT from baseline at 28 days and at 4 months.
 - Time to $\geq 50\%$ improvement in mSWAT.
 - Duration of response in skin (no progression after achieving $\geq 50\%$ improvement in mSWAT).
 - Change in pruritus medication utilization from baseline and incidence of pruritus medication utilization.

Safety and Tolerability Evaluations:

- Incidence and severity of clinically significant AEs (including grade 3 and 4 AEs, treatment-related AEs, SAEs, and AEs requiring discontinuation), physical examination findings, changes in electrocardiogram (ECGs), changes in laboratory parameters and changes in vital signs.
- Characterization of anti-drug antibody generation.

Pharmacokinetic Evaluation:

- Population PK parameters.
- During the crossover portion of the study
 - Pharmacokinetic C_{\max} and trough concentration analysis

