CMH	Cochran-Mantel-Haenzel
CR	Complete response
CRA	Clinical Research Associate
CRO	Contract Research Organization
CRR	Complete response rate
CT	Computed tomography
CTCAE	Common Terminology Criteria for Adverse Events
CTCL	Cutaneous T-cell lymphoma
CYP	Cytochrome P450
DMC	Data Monitoring Committee
ECG	Electrocardiogram
ECOG	Eastern Cooperative Oncology Group
eCRF	Electronic case report form
GLDH	Glutamate dehydrogenase
°F	Degree(s) Fahrenheit
FDA	Food and Drug Administration
FSH	Follicle-stimulating hormone
GCP	Good Clinical Practice
GGT	Gamma-glutamyl transferase
GLDH	Glutamate dehydrogenase
Ha	Alternative hypothesis
HDAC	Histone deacetylase

HEENT	Head, eyes, ears, nose, and throat
HIV	Human immunodeficiency virus
Ho	Null hypothesis
JAK	Janus kinase
IBM	Ideal body mass
ICF	Informed consent form
ICH	International Conference on Harmonization
IEC	Independent Ethics Committee
IND	Investigational New Drug
INR	International normalized ratio
IL	Interleukin
IRB	Institutional Review Board
ITT	Intent to Treat
IUD	Intrauterine device
IWRS	Interactive Web Response System
LDH	Lactate dehydrogenase
LNA	Locked nucleic acid
MedDRA	Medical Dictionary for Regulatory Activities
MF	Mycosis fungoides
miRNA	Micro ribonucleic acid
MRI	Magnetic resonance imaging
mRNA	Messenger ribonucleic acid
mSWAT	Modified Severity Weighted Assessment Tool
NCCN	National Comprehensive Cancer Network
NCI	National Cancer Institute
NK	Natural killer
ORR1	Objective response rate of at least 1 month duration
ORR4	Objective response rate of at least 4 months duration
PD	Pharmacodynamic(s)
PET	Positron emission tomography
PFS	Progression-free survival
PK	Pharmacokinetic(s)
PKAS	Pharmacokinetic Analysis Set
PPS	Per Protocol Set
PR	Partial response
PT	Prothrombin time
Q4W	Every 4 weeks
Q8W	Every 8 weeks
QTcF	QT interval corrected for heart rate using Fridericia's formula

RBC	Red blood cell(s)
RNA	Ribonucleic acid
ROA	Routes of administration
SAE	Serious adverse event
SAP	Statistical analysis plan
SC	Steering Committee
SS	Sézary syndrome
$t_{1/2}$	Terminal half-life
TEAE	Treatment-emergent adverse event
Th	T helper
T_{max}	Time to maximum plasma concentration
Treg	Regulatory T-cells
TSEBT	Total skin electron beam therapy
TSH	Thyroid-stimulating hormone
TTP	Time to progression
ULN	Upper limit of normal
US	United States
WBC	White blood cell(s)
WHO-DD	World Health Organization Drug Dictionary
WOCBP	Women of childbearing potential

PROTOCOL SYNOPSIS

Sponsor:	miRagen Therapeutics, Inc.

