Appendix F. Modified Severity Weighted Assessment Tool and Response Criteria

Derived from Olsen E, Whittaker S, Kim Y, et al. Clinical end points and response criteria in mycosis fungoides and Sézary syndrome: a consensus statement of the International Society for Cutaneous Lymphomas, the United States Cutaneous Lymphoma Consortium, and the Cutaneous Lymphoma Task Force of the European Organisation for Research and Treatment of Cancer. *J Clin Oncol* 2011; 29(18):2598-2607.

Table F1: Modified Severity Weighted Assessment Tool

Body Region	% BSA in Body Region	Assessment of Involvement in Subject's Skin		
		Patch ^a	Plaque ^b	Tumor ^c
Head	7			
Neck	2			
Anterior trunk	13			
Arms	8			
Forearms	6			
Hands	5			
Posterior trunk	13			
Buttocks	5			
Thighs	19			
Legs	14			
Feet	7			
Groin	1			
Subtotal of lesion BSA				
Weighting factor		×1	×2	×4
Subtotal lesion BSA x weighting factor				

NOTE: mSWAT score equals summation of each column line.

Abbreviations: BSA = body surface area; mSWAT = Modified Severity Weighted Assessment tool

- Any size lesion without induration or significant elevation above the surrounding uninvolved skin; poikiloderma may be present.
- Any size lesion that is elevated or indurated; crusting, ulceration, or poikiloderma may be present.
- Any solid or nodular lesion ≥ 1 cm in diameter with evidence of deep infiltration in the skin and/or vertical growth.

Table F2: Response in Skin Based on mSWAT Score

Response	Definition
CR	100% clearance of skin lesions ^a
PR	50%-99% clearance of skin disease from baseline without new tumors (T ₃) in patients with T ₁ , T ₂ or T ₄ only skin disease
SD	< 25% increase to < 50% clearance in skin disease from baseline without new tumors (T ₃) in patients with T ₁ , T ₂ , or T ₄ only skin disease
PD ^b	≥ 25% increase in skin disease from baseline or New tumors (T ₃) in patients with T ₁ , T ₂ or T ₄ only skin disease or Loss of response : in those with complete or partial response, increase of skin score of greater than the sum of nadir plus 50% baseline score
Relapse	Any disease recurrence in those with complete response

Abbreviations: CR = complete response; PD = progressive disease; PR = partial response; SD = stable disease

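### ORR1 is worded on the mSWAT percentage alone, so two visits that confirm progression by a new tumor can also count as an ORR1 response

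*Combined protocol and SAP*

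**What the plan says.** The primary endpoint in Section 3.2.1 is built on response categories: "Proportion of subjects achieving an objective skin response (complete response [CR] or partial response [PR]) of at least 4 months duration (ORR4"), with a pointer to Appendix F.

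ORR1, in Section 3.2.2, is built on a percentage: the proportion of subjects with at least 50% "improvement in mSWAT of at least 28-days duration (ORR1"). The bullet has no new-tumor condition and does not refer to Appendix F. The synopsis repeats it, and Section 3.2.2 repeats it for the crossover period. Section 12.4.4 lists the same 28-day, 50% summary without using the ORR1 label.

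Two other places point towards response categories. The abbreviation list expands ORR1 as "Objective response rate of at least 1 month duration". Section 7.5.1 states generally that response and progression are evaluated by the skin criteria in Appendix F.

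In Table F2 of Appendix F, partial response is "50%-99% clearance of skin disease from baseline without new tumors" in subjects with T1, T2 or T4 only skin disease. Progressive disease includes "increase in skin disease from baseline or New tumors" in the same subjects, whatever the score.

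Two related endpoints also use the percentage. One is "Time to $\geq 50\%$ improvement in mSWAT". The other is "Duration of response in skin (no progression after achieving" at least 50% improvement, so it begins at the percentage and ends at progression.

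**The concern.** ORR1 carries the name of a response rate but has the definition of a percentage change. Where the two part company, a subject can be a treatment failure under the response criteria and a success under ORR1 on the same evidence. Because confirmed progression is dated back to its first determination (Section 4.1), the PFS event and the start of the ORR1 response can fall on the same day.

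A reader will naturally take ORR1 as the 28-day counterpart of ORR4. As worded, the two differ in what counts as a response as well as in how long it must last. In the crossover period there is no concurrent control arm against which a more lenient definition would balance out. The trial is open-label, so the choice between the two definitions should be made before the data are seen.

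**Working it through.** No sample size, power or event count is at issue, so there is no plan figure to reproduce. The check is whether the definitions can conflict at the same visits, and where.

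**Inputs**
- mSWAT weights (Table F1): patch × 1, plaque × 2, tumor × 4, each applied to % body surface area (BSA).
- Literal ORR1 rule (3.2.2): score S ≤ 0.5 × baseline B, held for at least 28 days.
- Progression (Table F2): (a) an increase of at least 25% from baseline; (b) a new tumor in T1, T2 or T4 only disease; (c) after a response, a score above nadir + 0.5 × B.
- Confirmation of progression (4.1, 7.5.1.3): repeat mSWAT at 28 ± 3 days, with treatment continuing until then.
- Minimum mSWAT at Screening: 10. Planned arm size: 63 (12.5.1).

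**Step 1: which progression criteria can coexist with S ≤ 0.5B?**
- (a) needs S ≥ 1.25B. Impossible.
- (c) needs S > nadir + 0.5B, which is at least 0.5B because the nadir cannot be negative. Impossible.
- (b) sets no lower limit on the score. Possible.

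An enumeration over baselines 10 to 200 in steps of 2, with every integer score and nadir from 0 to 0.5B, gave 0 coexisting cases for (a) and 0 for (c). Only the new-tumor criterion can conflict.

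**Step 2: worked cases, tumor-free at baseline**
- Patch on 40% BSA: B = 40. At Week 9, patch 12% and a new tumor on 1%: S = 12 + 1 × 4 = 16. Improvement = 1 − 16/40 = 60%. Unchanged at Week 13.
- Patch 20% and plaque 20%: B = 20 + 2 × 20 = 60. Later patch 10%, plaque 5%, new tumor 1%: S = 10 + 10 + 4 = 24. Improvement = 1 − 24/60 = 60%.

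In the first case Table F2 gives progression at Week 9, confirmed at Week 13. The literal ORR1 wording gives a response from Week 9 to Week 13. Duration of response starts and ends at Week 9, so it is zero or undefined.

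**Step 3: limits of the conflict**
- Tumor area t alone contributes 4t, so S ≤ 0.5B requires t ≤ B/8: 10/8 = 1.25% BSA at B = 10, 40/8 = 5% at B = 40, and 60/8 = 7.5% at B = 60. Residual patch or plaque lowers these limits.
- Subjects with T3 disease at baseline are outside it, because Table F2 does not make a new tumor progression for them.
- A repeat at day 25 to 27 can confirm progression without literally spanning 28 days. Where the tumor is present from the first 50% visit, the overlap therefore needs a repeat at day 28 to 31.

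**Step 4: size**
One subject in 63 is 1/63 = 1.6 percentage points of ORR1 in that arm. The documents give no rate of new tumors among subjects with at least 50% improvement, so the number affected cannot be computed and may be zero.

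**The case against.** The strongest reply is that Section 7.5.1 already sets the general rule. Response is evaluated by Appendix F, Table F2 requires no new tumors for a partial response in these subjects, and the abbreviation list calls ORR1 an objective response rate. On that reading the example subject has progressed and is not a responder. This stands as a defensible reading, so it would be too strong to say that such subjects will be counted as responders. It does not settle the matter, because a general pointer does not override an explicit endpoint definition that omits the condition. Section 12.4.4 also displays duration of response separately from duration of at least 50% improvement, so the plan itself treats them as different things. Two programmers could each defend a different ORR1.

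The percentage measures may also be deliberate. For time to at least 50% improvement this stands: it does what its name says and is not called a response. It does not explain giving a percentage measure the name of a response rate.

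The consequence is small, and this stands too. Section 12.2 names only PFS as key secondary, and Section 12.4.4 calls secondary p-values supportive. Details of secondary endpoints are deferred to a SAP due before database lock. The documents contain no separate SAP definition of ORR1, so whether the deferred SAP resolves the point cannot be judged.

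Three stronger inferences are tempting but unsupported:
- That duration of response ignores new tumors. It ends at progression, which includes them; only its start uses the bare percentage.
- That every tumor-free subject who clears flat disease while developing a tumor is misclassified. The net score, with the tumor weighted by 4, must still be at least 50% below baseline and stay there for 28 days. A subject who completes a tumor-free 28-day response and progresses later is a true responder.
- That several subjects per arm are affected. No passage supports any count.

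**Conclusion.** The point holds as a conflict of definition in a supportive secondary endpoint. Under the literal wording, a subject with T1, T2 or T4 only disease can have confirmed progression by a new tumor and an ORR1 response from the same two visits, with a duration of response that is zero or undefined. This rests on reading the ORR1 bullet as written and on a net score that stays at or below half of baseline with the tumor included. The effect is 1.6 points per affected subject in an arm of 63, with an unknown and possibly zero number of subjects.

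A reader might infer that the main results are at risk. They are not: ORR4 is defined by CR or PR, and the PFS definition and the sample size do not use ORR1. The change is still worth making, because ORR1 is a named endpoint in both periods and its name and definition disagree.

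**What to change.** In Section 3.2.2, the synopsis and Section 12.4.4, for both the randomized and crossover periods:

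- Define ORR1 as CR or PR by Table F2, including the absence of new tumors in T1, T2 or T4 only disease, held for at least 28 days (± 3).
- Start duration of response in skin at the first such CR or PR, and keep its end at progression.
- Keep time to at least 50% improvement and the other at-least-50% mSWAT measures as separately named percentage endpoints, not labelled as response.

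The cost is wording and programming only, since Table F2 already requires new tumors to be identified. The downside is that ORR1 may be slightly lower than under the present wording.
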